3.0 STUDY IMPLEMENTATION

This is a phase 1 /2 study of everolimus and sorafenib in patients with recurrent high-grade gliomas. Patients must initiate study treatment within 96 hours after registration.

All patients will be monitored for hematologic or serologic evidence of myelosuppression, hepatic injury, renal injury, and electrolyte disturbances and for clinical evidence of other toxicity as is described in section 3.5.

3.1 PHASE 1 STUDY DESIGN

3.1.1 Drug Administration

Patients will be treated with daily everolimus (days 1-28) in combination with sorafenib (as per the table below).

The schedule providing highest dose without DLT (as defined above) will be used as the phase II dose. The dose levels are listed in Table 3-11.

There is not a defined set maximum number of cycles that a patient may have. Patients may continue with protocol therapy until criteria for “Off Treatment” is met. Off treatment criteria could be any of the following events/reasons; disease progression, intolerable side effects (toxicities) and/or withdrawal from study.

3.1.2 Dose Escalation

Patients will be treated at the dose levels in Table 3-11 starting at dose level 1. Initially everolimus and sorafenib will be administered continuously. If two DLTs are encountered at the first dose level (sorafenib 400 mg twice daily and everolimus 5 mg daily) the dose for the next cohort of patients will be decreased to sorafenib 400 mg twice daily 7 days on, 7 days off and everolimus 5 mg daily (dose level -1). If dose level -1 is tolerated, dose escalations will occur along the “b” pathway (-1, 1b, 2b, 3b, 4b).

If two DLTs are encountered at dose level 2, the dose for the next cohort of patients will be reduced to sorafenib 400 twice daily, 7 days on 7 days off and everolimus 7.5 mg daily (dose level 1b). Subsequent dose escalations will occur along the “b” pathway (2, 1b, 2b, 3b, 4b).

The study drugs will be self-administered (by the patients themselves). The investigator will instruct the patient to take the study drug exactly as specified in the protocol. Patients will be instructed to take the study drugs in the morning, at the same time each day.

The study drugs must be taken 1 hour before or two hours after food. Consumption of grapefruit juice should be avoided while taking the study drugs. If vomiting occurs, no attempt should be made to replace a dose.

All dosages prescribed and dispensed to the patient and all dose changes during the study must be recorded.

Table 3-1: Phase I dosing table.

DOSE LEVEL	SORAFENIB	EVEROLIMUS
-1	400 mg BID,	5 mg daily

DOSE LEVEL	SORAFENIB	EVEROLIMUS
	7 days on 7 days off	
1	400 mg BID	5 mg daily
2	400 mg BID	7.5 mg daily
3	400 mg BID	10 mg daily
4	600 mg BID	10 mg daily
1b	400 mg BID, 7 days on 7 days off	7.5 mg daily
2b	400 mg BID, 7 days on 7 days off	10 mg daily
3b	600 mg BID, 7 days on 7 days off	10 mg daily
4b	800 mg BID, 7 days on 7 days off	10 mg daily

Note: On the sorafenib 7 days on 7 days off schedule, sorafenib will be given on days 1-7 and 15-21.

The MTD will be based on the assessment of DLT during the first 28 days of treatment only (cycle-1), and will be defined as the dose at which fewer than one-third of patients experience a DLT to one of the study drugs. The MTD is the dose level at which 0/6 or 1/6 patients experience DLT with the next higher dose having at least 2/3 or 2/6 patients encountering DLT. Three patients will be treated at each dose level. If one dose limiting toxicity (DLTs) is encountered an additional 3 patients will be added to that dose level. If at any point two DLTs are encountered within a given dose level, then the MTD has been exceeded and three more patients are treated at the next lower dose (if only three patients were previously treated at that prior dose).

3.1.3 Dose-Limiting Toxicity

Toxicities will be graded according to the NCI Common Terminology Criteria for Adverse Events (CTCAE) version 4.0. If multiple toxicities are seen, the presence of DLT should be based on the most severe toxicity experienced. DLT will be defined as any of the following events occurring during treatment with sorafenib and/or everolimus and attributable to one of the study drugs:

- 3.1.3.1 Any grade 3 thrombocytopenia, grade 4 anemia, grade 4 neutropenia, or febrile neutropenia of any grade.
- 3.1.3.2 Any non-hematologic grade 3 or grade 4 toxicity, excluding alopecia and/or hand/foot reaction.
- 3.1.3.3 Failure to recover from toxicities (to grade 1 or less) to be eligible for re-treatment with sorafenib and everolimus within 14 of the last dose of sorafenib and everolimus.

3.2 PHASE II STUDY DESIGN

3.2.1 Drug Administration

All patients treated on the phase II cohorts will receive a combination of sorafenib (7 days on, 7 days off) and everolimus daily over a 28-day cycle, as follows:

Sorafenib 400 mg BID PO (days 1-7 and days 15-21)

Everolimus 5 mg PO daily (days 1-28)

There is not a defined set of maximum number of cycles that a patient may have. Patients may continue with protocol therapy until criteria for “Off Treatment” is met. See Section **3.7.1**.

3.3 DOSE MODIFICATIONS IN PHASE I (POST CYCLE 1) AND PHASE II

Patients with stable or responding disease may be retreated at the same dose or at a reduced dose level, depending upon the adverse events observed in the current cycle and any adverse events (based on the CTCAE v.4) present on the first day of the next cycle. If multiple toxicities are seen, the dose administered in a subsequent cycle should be based on the most severe toxicity experienced in the current cycle.

Patients who experience toxicity should have laboratory testing at least weekly until the toxicity has resolved.

Toxicities will be graded according to the NCI Common Terminology Criteria for Adverse Events (CTCAE) version 4.0. If multiple toxicities are seen, the toxicity should be based on the most severe toxicity experienced. Toxicities will be defined as any of the following events occurring during treatment with sorafenib and/or everolimus and attributable to one of the study drugs:

- A. Any grade 3 thrombocytopenia, grade 4 anemia, grade 4 neutropenia, or febrile neutropenia of any grade.
- B. Any non-hematologic grade 3 or grade 4 toxicity, excluding alopecia and/or hand/foot reaction.
- C. Failure to recover from grade 3 or 4 toxicities (to grade 1 or less) to be eligible for re-treatment with sorafenib and everolimus within 14 of the last dose of sorafenib and everolimus.

3.3.1 Within Treatment Cycles

If a patient experiences toxicities during a treatment cycle, the treatment will be immediately suspended until a grade 1 or less toxicity. If the toxicity resolves to less than or equal to grade 1 within 2 weeks, the patient will be retreated at the dose level described in Table **3-2** below. (Refer to Table **3-6** and Table **3-7** for management of everolimus-induced toxicities and Table **3-8**, Table **3-9** and Table **3-10** for management of sorafenib-induced toxicities.) If toxicity persists, the patient should be taken off study.

Two dose reductions are permitted. Doses that are reduced for sorafenib or everolimus related toxicity will not be re-escalated, even if there is minimal or no toxicity with the reduced dose. Patients whose dose has been reduced for adverse events that are subsequently not felt to be related to sorafenib or everolimus may have the dose re-escalated after completion of one cycle with toxicities less than or equal to grade 1. If any patient has further toxicities that would require additional reductions, or if treatment is held for more than 2 consecutive weeks because of ongoing

toxicity, the Study PI will assess if the patient should remain in the study (if the patient has benefited from treatment).

Table 3-2: Dose Modification Table

DOSE LEVEL	SORAFENIB	EVEROLIMUS
1 (starting dose)	400 mg BID 7 days on 7 days off	5 mg daily
-1	400 mg AM dose 200 mg PM dose 7 days on 7 days off	5 mg daily
-2	200 mg AM dose 200 mg PM dose 7 days on 7 days off	5 mg daily

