3.3.1.1 Hematologic Toxicity

Dose Modifications Based on ANC and Platelet Counts obtained weekly for Phase I and every 2 weeks for Phase II (**sorafenib or everolimus**): Please note per CTCAE v 4, ANC 750-999 falls within grade 3 adverse event and Platelets 50,000 to <75,000 is grade 2.

ANC (/mL)	Platelets (/mL)	% of Dose Planned
> 1000	and > 75,000	100%
750-999(G3)	or 50,000 to < 75,000(G2)	hold*
< 750	or < 50,000 (G3-G4)	hold**

* Suspect drug should be held. Upon recovery to ANC \geq 1,500/mL and platelets to \geq 100,000/mL, the same dose level will be administered.

** Suspect drug should be held. Upon recovery to ANC \geq 1,500/mL and platelets to \geq 100,000/mL, one lower dose levels will be administered.

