3.3.1.2 Non-hematologic Toxicity

Dose Modifications

Based on **sorafenib or everolimus** -Related Non-Hematologic Toxicities:

CTCAEv.4 Grade	% of Dose Planned
0-2+	100%+
3*	hold**
4	hold***

+For symptomatic Grade 2 toxicity, the suspect drug dose may be held at the discretion of the local investigator until recovery to CTCAE Grade 0-1, then resume at one dose lower.

*Except nausea/vomiting (unless patients are on optimal antiemetic therapy)

**Hold suspect drug until recovery to CTCAE Grade 0-1 (or to within 1 grade of starting values for pre-existing laboratory abnormalities), and then resume at one dose level lower.

***Hold suspect drug until recovery to CTCAE Grade 0-1 (or to within 1 grade of starting values for pre-existing laboratory abnormalities), and then resume at two dose levels lower.

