3.3.4 Management of hyperlipidemia

Everolimus causes hyperlipidemia. Treatment of hyperlipidemia should take into account the pre-treatment status and dietary habits. Blood tests to monitor hyperlipidemia must be taken in the fasting state. Grade 2 or higher hypercholesterolemia (>300 mg/dL or 7.75 mmol/L) or grade 2 or higher hypertriglyceridemia (>2.5 x upper normal limit) should be treated with a statin or appropriate lipid-lowering medication, in addition to diet. Patients should be monitored clinically and through serum biochemistry for the development of rhabdomyolysis and other adverse events as required in the product label/data sheets for HMG-CoA reductase inhibitors. Please refer to section 3.3.1.2 for dose modifications of everolimus.

Note: Concomitant therapy with fibrates and an HMG-CoA reductase inhibitor is associated with an increased risk of a rare but serious skeletal muscle toxicity manifested by rhabdomyolysis, markedly elevated creatine kinase (CPK) levels and myoglobinuria, acute renal failure and sometimes death. The risk versus benefit of using this therapy should be determined for individual patients based on their risk of cardiovascular complications of hyperlipidemia.

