3.3.7 Management of suspected everolimus toxicity

Table 3-7: Criteria for dose-modification in case of suspected everolimus toxicity and re-initiation of everolimus treatment

Toxicity	Actions

Non-hematological toxicity
 
Grade 2 (except pneumonitis – refer to Table 3-6)
 
Grade 3 (except hyperlipidemia*) (except pneumonitis – refer to Table 3-6)
 
Grade 4
	
If the toxicity is tolerable to the patient, maintain the same dose. If the toxicity is intolerable to patient, interrupt everolimus until recovery to grade ≤1. Then reintroduce everolimus at same dose. If event returns to grade 2, then interrupt everolimus until recovery to grade ≤1. Then reintroduce everolimus at same dose level.
 
Interrupt everolimus until recovery to grade ≤1. Then reintroduce everolimus at same dose level. For pneumonitis consider the use of a short course of corticosteroids.
 
Discontinue everolimus.

Hematological toxicity
 
Grade 2 Thrombocytopenia (platelets <75, ≥ 50x10⁹/L)
 
Grade 3 Thrombocytopenia (platelets <50, ≥ 25 x10⁹/L)
 
Grade 4 Thrombocytopenia (platelets < 25 x10⁹/L)
	
Interrupt everolimus until recovery to grade ≤1 (>75 x10⁹/L). Then reintroduce everolimus at initial dose. If thrombocytopenia again returns to grade 2, interrupt everolimus until recovery to grade ≤1. Then reintroduce everolimus at same dose level.
 
Interrupt everolimus until recovery to grade ≤1 (platelets ≥ 75 x10⁹/L). Then resume everolimus at same dose level. If grade 3 thrombocytopenia recurs, discontinue everolimus.
 
Discontinue everolimus.

Toxicity	Actions
Grade 3 Neutropenia (neutrophils $<1, \geq 0.5 \times 10^9/L$)	Interrupt everolimus until recovery to grade ≤ 1 (neutrophils $\geq 1.5 \times 10^9/L$). Then resume everolimus at the initial dose. If ANC again returns to Grade 3, hold everolimus until the ANC $\geq 1.5 \times 10^9/L$. Then resume everolimus dosing at same dose level. Discontinue patient from study therapy for a third episode of grade 3 neutropenia.
Grade 4 Neutropenia (neutrophils $< 0.5 \times 10^9/L$)	Interrupt everolimus until recovery to grade ≤ 1 (neutrophils $\geq 1.5 \times 10^9/L$). Then resume everolimus at the lower dose level. If grade 3 or grade 4 neutropenia occurs despite this dose reduction, discontinue everolimus.

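### After grade 3 thrombocytopenia the protocol gives opposite restart instructions for platelet counts from 75 to 99 x10^9/L, and its rule for grade 3 hyperlipidemia contradicts itself

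*Combined protocol and SAP*

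**What the plan says.** Section 3.3 lists what counts as a toxicity when attributable to a study drug. Item A includes grade 3 thrombocytopenia. Item B reads "Any non-hematologic grade 3 or grade 4 toxicity, excluding alopecia and/or hand/foot reaction".

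- **3.3.1:** for such an event "the treatment will be immediately suspended until a grade 1 or less toxicity". If it resolves within 2 weeks, "the patient will be retreated at the dose level described in Table" 3-2. The section also points to Tables 3-6 and 3-7 for everolimus and to Tables 3-8 to 3-10 for sorafenib.
- **3.3.1.1**, written for either drug: below 50,000 platelets the suspect drug is held, and on recovery to at least "100,000/mL, one lower dose levels will be administered". From 50,000 to under 75,000 it is also held to 100,000, but restarts at the same level.
- **3.3.1.2**, also for either drug: for grade 3, "Hold suspect drug until recovery to CTCAE Grade 0-1", then one level lower. The only grade 3 exception is nausea and vomiting, unless the patient is already on optimal antiemetics.
- **Table 3-7** (everolimus): for grade 3 non-hematologic events other than pneumonitis and hyperlipidemia, "interrupt everolimus until recovery to grade ≤1. Then reintroduce everolimus at same dose level". The same words cover recurrent grade 2 thrombocytopenia. Grade 3 thrombocytopenia resumes at 75 x10^9/L, same level. A footnote sends grade 3 hyperlipidemia to 3.3.4.
- **3.3.4:** "Please refer to section 3.3.1.2 for dose modifications of everolimus".
- **Table 3-9** (sorafenib): grade 3 hematologic toxicity restarts below grade 2, one level lower. Its footnote lets certain grade 3 events continue uninterrupted at the investigator's discretion.

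**The concern.** These rules have to be applied at the bedside, at once. If two of them give a hold and a restart for the same platelet count, whatever the investigator does breaks one. Section 6.1.8 treats any departure from the protocol as a deviation, and 6.3.1 makes every deviation reportable within 7 days, so the conflict also creates reporting with no clear right answer. What is at stake is dosing safety and drug exposure.

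**Working it through.** The plan states no computed figure on this point, so the check sets the rules side by side.

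**Units.** Section 3.3.1.1 prints its counts per mL. I read them as per mm3, so 100,000 is 100 x10^9/L. The protocol supports this: 3.3.1.1 places the boundary between grades 2 and 3 at 50,000, and Table 3-7 places it at 50 x10^9/L.

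**Meaning of below grade 2 in Table 3-9.** The grading note in 3.3.1.1 says "Platelets 50,000 to <75,000 is grade 2", so a grade below 2 starts at 75,000. Table 3-7 likewise equates grade 1 or less with at least 75 x10^9/L.

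**Grade 3 thrombocytopenia** (platelets in x10^9/L):

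| Rule | What is held | Restart at | Restart level |
|---|---|---|---|
| 3.3.1 | the treatment | grade 1 or less (75) | Table 3-2, level not named |
| 3.3.1.1 | suspect drug | 100 | one lower |
| Table 3-7 | everolimus | 75 | same |
| Table 3-9 | sorafenib | below grade 2 (75) | one lower |

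Gap in threshold: 100 - 75 = 25 x10^9/L; 25/75 = 33%. Illustration: everolimus-attributed platelets fall to 40 and recover to 80. Table 3-7 restarts everolimus; 3.3.1.1 keeps it on hold.

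**Grade 2 thrombocytopenia attributed to everolimus.** Section 3.3.1.1 needs at least 100; Table 3-7 needs more than 75. Neither reduces the dose on first restart, so only the threshold differs. Table 3-9 does not interrupt sorafenib for grade 2, so it has no grade 2 recovery threshold to compare.

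**Grade 3 hyperlipidemia attributed to everolimus.** Table 3-7 exempts it from interruption and points to 3.3.4. Section 3.3.4 points to 3.3.1.2. Section 3.3.1.2 holds the suspect drug at grade 3 and does not except hyperlipidemia. Following the cross-references leads from an exemption to a hold.

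**Table 3-9 footnote.** Grade 3 fever/chills, transaminases below 10 times ULN, and hyperlipidemia or hyperamylasemia without pancreatitis are item B events. None is excepted in item B, 3.3.1 or 3.3.1.2. An investigator who uses the permission departs from those rules; one who holds satisfies all of them.

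**Restart level after other everolimus-attributed grade 3 non-hematologic events** (not pneumonitis or hyperlipidemia). Section 3.3.1.2 says one level lower, Table 3-7 the same level. Table 3-2 gives everolimus 5 mg at levels 1, -1 and -2, so the everolimus difference is 5 - 5 = 0 mg. A step from level 1 to -1 changes only sorafenib, from 400 + 400 = 800 mg to 400 + 200 = 600 mg on a dosing day.

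**The case against.** The best defense is that 3.3.1 is a general rule, its subsections and the tables it cites supply the detail, and the drug-specific table governs. Questions go to the Study Chair or the research nurse (end of 3.3.9), and the team discusses each patient every other week (6.7.1).

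Much of this stands, and it rules out several stronger readings:

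- A reader might infer that stopping the treatment in 3.3.1 and holding only the suspect drug in 3.3.1.1 and 3.3.1.2 are incompatible. The subsections can fairly be read as spelling out the general sentence. Clearer wording is worthwhile, but this is not a contradiction.
- A reader might infer that the Table 3-9 footnote mandates full-dose sorafenib where 3.3.1.2 mandates a hold and reduction. The footnote is permissive and silent on dose, so no milligram difference follows from it.
- A reader might infer that every everolimus-attributed grade 3 event restarts at conflicting levels. Grade 3 pneumonitis goes to Table 3-6, which also restarts one level lower.

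The defense does not settle the platelet conflict or the hyperlipidemia loop. No text says the tables prevail. Sections 3.3.1.1 and 3.3.1.2 are themselves written for both drugs, and 3.3.3 to 3.3.5 send everolimus toxicities back to 3.3.1.2, so that section is plainly meant to operate. A contact for questions does not decide between two written rules, though it does limit the practical risk.

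**Conclusion.** The concern holds for two contradictions. After attributable grade 3 thrombocytopenia, counts from 75 to 99 x10^9/L get opposite restart instructions for either drug; the threshold mismatch also covers grade 2 events attributed to everolimus. Grade 3 hyperlipidemia is both exempted from interruption and routed to a hold. The footnote exceptions and the everolimus restart level are lesser inconsistencies, the latter with no change in everolimus dose.

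This rests on the unit reading and on the protocol's own grading note. The documents give no event rate, so no number of affected patients can be stated. Section 2.4 marks Phase I and Groups A and C as closed, and 9.4 says subjects at non-NCI sites were off treatment at Amendment C, so the reach is mainly Group B patients still on treatment. A reader might infer differences between sites or bias in PFS3 or PFS6; nothing in the documents shows either. It should be corrected, but it does not undermine the trial's design.

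**What to change.** 1. Use one platelet recovery threshold, at least 100 x10^9/L as in 3.3.1.1, for grades 2 and 3 in Table 3-7 and grade 3 in Table 3-9. State in 3.3.1 that platelets follow this count rather than the grade.
2. In 3.3 item B, 3.3.1 and 3.3.1.2, except grade 3 hyperlipidemia as in Table 3-7, and the Table 3-9 footnote events when attributed to sorafenib. Carry the existing 3.3.1.2 nausea and vomiting exception into item B and 3.3.1.
3. In 3.3.1, say that the suspect drug is held, and both drugs if the event is attributed to both or attribution is unclear.
4. Have the sponsor state whether one level lower in Table 3-2 applies to events attributed only to everolimus. Keep the one-level reduction for grade 3 pneumonitis in Table 3-6. A blanket statement that sorafenib is never reduced for everolimus-only events would contradict that table, because everolimus stays at 5 mg throughout Table 3-2.

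The cost is wording, with no new data or analysis. The higher threshold lengthens some holds and may bring some patients up against the 2-week limit in 3.3.1. The sponsor must confirm that the 100 x10^9/L threshold and suspect-drug holding are the intended policy. Using 75 throughout would also remove the platelet conflict, at the price of earlier restarts.

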3.3.1.1 Hematologic Toxicity

Dose Modifications Based on ANC and Platelet Counts obtained weekly for Phase I and every 2 weeks for Phase II (**sorafenib or everolimus**): Please note per CTCAE v 4, ANC 750-999 falls within grade 3 adverse event and Platelets 50,000 to <75,000 is grade 2.

ANC (/mL)	Platelets (/mL)	% of Dose Planned
> 1000	and > 75,000	100%
750-999(G3)	or 50,000 to < 75,000(G2)	hold*
< 750	or < 50,000 (G3-G4)	hold**

* Suspect drug should be held. Upon recovery to ANC \geq 1,500/mL and platelets to \geq 100,000/mL, the same dose level will be administered.

** Suspect drug should be held. Upon recovery to ANC \geq 1,500/mL and platelets to \geq 100,000/mL, one lower dose levels will be administered.

3.3.1.2 Non-hematologic Toxicity

Dose Modifications

Based on **sorafenib or everolimus** -Related Non-Hematologic Toxicities:

CTCAEv.4 Grade	% of Dose Planned
0-2+	100%+
3*	hold**
4	hold***

+For symptomatic Grade 2 toxicity, the suspect drug dose may be held at the discretion of the local investigator until recovery to CTCAE Grade 0-1, then resume at one dose lower.

*Except nausea/vomiting (unless patients are on optimal antiemetic therapy)

**Hold suspect drug until recovery to CTCAE Grade 0-1 (or to within 1 grade of starting values for pre-existing laboratory abnormalities), and then resume at one dose level lower.

***Hold suspect drug until recovery to CTCAE Grade 0-1 (or to within 1 grade of starting values for pre-existing laboratory abnormalities), and then resume at two dose levels lower.

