3.3.8 Management of sorafenib induced skin toxicity

It is common for patients treated with sorafenib to experience skin toxicity (rash/desquamation, hand/foot reaction, etc.). Guidelines for management are specified in the table below.

Table 3-8: Guidelines for management of sorafenib induced skin toxicity

Skin Toxicity Grade	Occurrence	Suggested Dose Modification
Grade 1: Numbness, dysesthesia, paresthesia, tingling, painless swelling, and erythema or discomfort of the hands or feet which does not disrupt the patient's normal activities.	Any occurrence	Continue treatment with sorafenib and consider topical therapy for symptomatic relief.
Grade 2: Painful erythema and swelling of the hands or feet and/or discomfort affecting the patient's normal activities.	First occurrence	Continue treatment with sorafenib and consider topical therapy for symptomatic relief. If no improvement within 7 days, see below.
	No improvement within 7 days or 2 nd occurrence	Interrupt sorafenib treatment until toxicity resolves to Grade 0-1. When resuming treatment, decrease sorafenib dose by one dose level.
	Third occurrence	Interrupt until resolved to grade 0-1. When resuming treatment, decrease dose by two dose levels (from the starting dose).
Grade 3: Moist desquamation, ulceration, blistering or severe pain of the hands or feet, or severe discomfort that causes the patient to be unable to work or perform activities.	First occurrence	Interrupt sorafenib treatment until toxicity resolves to Grade 0-1. When resuming treatment, decrease sorafenib by one dose level.
	Second occurrence	Interrupt until resolved to grade 0-1. When resuming treatment, decrease dose by two dose levels (from the starting dose).
	Third occurrence	Discontinue sorafenib treatment.

Table 3-9: Dose Modifications for Sorafenib-Associated Toxicity¹

Toxicity	Grade 1	Grade 2	Grade 3*	Grade 4*
Non-hematologic	Continue at the same dose level.	Continue at the same dose level.	Withhold dose until toxicity is < 1. When resuming treatment reduce dose by one dose level.	Discontinue treatment.
Hematologic	Continue at the same dose level.	Continue at the same dose level.	Withhold dose until toxicity is grade <2. When resuming treatment reduce dose by one dose level.	Withhold dose until toxicity is grade <2. When resuming treatment reduce dose by two dose levels.

¹ See separate suggestions for dose modification due to hand-foot skin reactions.

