*Patients who develop grade 3 fever/chills, grade 3 elevation of hepatic transaminases with ALT and AST <10X ULN, grade 3 hyperlipidemia or hyperamylasemia without clinical or other evidence of pancreatitis, grade 3 leukopenia, or grade 3/grade 4 lymphopenia may continue study treatment without interruption at the discretion of the investigator.

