3.3.9 Hypertension: Dose Modifications of Sorafenib for Hypertension

Hypertension is a known and potentially serious adverse event associated with sorafenib treatment. Patients will have their blood pressure monitored and recorded weekly during the Cycle 1 and then every cycle of the entire treatment period, either at the doctor's office or by using any calibrated electronic device (such as those found at a local drug store or pharmacy). Patients will have a Blood Pressure Diary on which to record the measurements, which will be kept with research chart. If the patient's blood pressure is elevated at any time (>140/100), even outside clinic visits, they should contact their treating physician.

Table 3-10: Dose modifications for Sorafenib-associated hypertension

Grade (CTCAE v 4.0)	Antihypertensive Therapy	Blood Pressure Monitoring	Sorafenib Dose
Grade 1	None	Routine	No change
Grade 2 (asymptomatic)	Initiate monotherapy (suggest dihydropyridine calcium-channel blocker)	Increase frequency and monitor (by health professional) every 2 days until stabilized	No change
Grade 2 (symptomatic/persistent) OR Diastolic BP > 110 mm Hg OR Grade 3	Add agent(s): Ca ⁺⁺ channel blocker (if not already used), K ⁺ channel opener (angiotensin blockers), beta-blocker, thiazide diuretic	Increase frequency and monitor (by health professional) every 2 days until stabilized; continue qod monitoring to stabilization after dosing restarted.	Hold* Sorafenib until symptoms resolve and diastolic BP < 100 mm/Hg. Resume treatment at 1 dose level lower**
Grade 4			Off protocol therapy

* Patients requiring a delay of > 28 days should go off protocol therapy unless, in the treating physician's opinion, the patient may benefit from continued treatment.
 
** Patients requiring >2 dose reductions should go off protocol therapy.
			

CTCAE v 4.0 definitions
 
Grade 1: asymptomatic, transient (<24 hrs) increase by > 20 mmHg (diastolic) or > 150/100 if previously WNL; intervention not indicated
 
Grade 2: recurrent or persistent (>24 hrs) or symptomatic increase by >20 mmHg (diastolic) or to >150/100 if previously WNL; monotherapy may be indicated.
 
Grade 3: requiring more than one drug or more intensive therapy than previously
 
Grade 4: life threatening (e.g., hypertensive crisis)
			

For treatment or dose modification related questions, please contact the Study Chair or the BTTC Coordinating Center's Research Nurse.

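### After some grade 4 events the general dose rules restart a drug that the drug-specific tables stop, and everolimus has no dose level below 5 mg

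*Combined protocol and SAP*

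**What the plan says.** Section 3.3.1 allows two dose reductions along Table 3-2. It refers readers to Tables 3-6 and 3-7 for everolimus toxicity and to Tables 3-8 to 3-10 for sorafenib toxicity.

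**General rules, for either drug**
- Section 3.3.1.2: after grade 4 non-hematologic toxicity the suspect drug is held until recovery "and then resume at two dose levels lower".
- Section 3.3.1.1: after ANC below 750 or platelets below 50,000 the suspect drug is held, and on recovery "one lower dose levels will be administered". After ANC 750-999, on recovery "the same dose level will be administered".

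**Drug-specific tables**
- Table 3-7 (everolimus): grade 4 non-hematologic toxicity, grade 4 thrombocytopenia and grade 4 febrile neutropenia all read "Discontinue everolimus". Grade 4 neutropenia restarts at a lower level.
- Table 3-9 (sorafenib): grade 4 non-hematologic toxicity reads "Discontinue treatment". Grade 4 hematologic toxicity is withheld, then "When resuming treatment reduce dose by two dose levels". Grade 3 hematologic toxicity restarts one level lower. Under a footnote, patients with certain listed events "may continue study treatment without interruption at the discretion of the investigator".
- Table 3-6 also stops treatment at grade 4 pneumonitis, and Table 3-10 at grade 4 hypertension gives "Off protocol therapy".

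Table 3-2 lowers sorafenib at levels -1 and -2 but leaves everolimus at 5 mg daily throughout. Sections 3.3.3, 3.3.4 and 3.3.5 (stomatitis, hyperlipidemia, hyperglycemia) send the reader back to 3.3.1.2 for dose changes.

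**The concern.** Both sets of rules stop dosing during the event. They part on what follows. A site that follows 3.3.1.2 may re-expose a patient, after a grade 4 event, to a drug that the matching table says should not be given again. Two sites could treat the same event differently and both be following the protocol.

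The second gap concerns everolimus. Sections 3.3.1.1 and 3.3.1.2, Table 3-6 (grade 2 and 3 pneumonitis) and Table 3-7 (grade 4 neutropenia) all ask for a lower everolimus dose. The Phase II starting dose is 5 mg, and the reduction table offers nothing beneath it. A reduction ordered because of everolimus toxicity therefore cannot lower everolimus.

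**Working it through.** The plan gives no figure to reproduce here. The check sets the rules side by side and then works out the exposure that follows from Table 3-2.

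**1. Action after recovery**

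| Event | Section 3.3.1.1 or 3.3.1.2 | Drug table | Difference |
|---|---|---|---|
| Everolimus, grade 4 non-hematologic | restart, two levels lower | stop (3-7; 3-6 for pneumonitis) | restart v stop |
| Sorafenib, grade 4 non-hematologic | restart, two levels lower | stop (3-9; 3-10 for hypertension) | restart v stop |
| Everolimus, grade 4 thrombocytopenia | restart, one level lower | stop (3-7) | restart v stop |
| Everolimus, grade 4 febrile neutropenia | restart, one level lower (ANC row) | stop (3-7) | restart v stop |
| Everolimus, grade 4 neutropenia | restart, one level lower | restart at a lower level (3-7) | none |
| Sorafenib, grade 4 neutropenia or thrombocytopenia | restart, one level lower | restart, two levels lower (3-9) | size of reduction |
| Sorafenib, ANC 750-999 (grade 3) | restart, same level | restart, one level lower (3-9) | size of reduction |

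Of the six grade 4 entries, four are restart against stop, one differs in size, and one agrees.

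**2. Sorafenib per 28-day cycle** (Table 3-2; 14 dosing days, days 1-7 and 15-21)
- Level 1: 14 × 800 = 11,200 mg
- Level -1: 14 × 600 = 8,400 mg
- Level -2: 14 × 400 = 5,600 mg

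Starting from level 1:
- Grade 4 neutropenia or thrombocytopenia: 8,400 mg under 3.3.1.1, 5,600 mg under Table 3-9. The table dose is 1 − 5,600/8,400 = 33% lower.
- ANC 750-999: 11,200 mg against 8,400 mg. The table dose is 1 − 8,400/11,200 = 25% lower.

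**3. Everolimus per cycle** (28 dosing days)
- Levels 1, -1 and -2: 28 × 5 = 140 mg each, a change of 0%.
- For comparison, with the 2.5 mg tablet listed in 10.2.5: 28 × 2.5 = 70 mg, 50% lower.

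If everolimus toxicity calls for two levels lower and only the suspect drug is changed, neither dose falls. If the whole Table 3-2 row is applied, everolimus still does not fall, and sorafenib falls by 1 − 5,600/11,200 = 50% for a toxicity attributed to the other drug.

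**4. Precedence.** Section 3.3.1 points forward to the tables; 3.3.3 to 3.3.5 point back to 3.3.1.2. For example, grade 4 hyperglycemia attributed to everolimus is sent by 3.3.5 to the restart rule, while Table 3-7 stops the drug. No sentence settles which prevails.

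**The case against.** **The specific rule should beat the general one.** Section 3.3.1 directs sites to the drug tables, and many investigators would read it that way. That is plausible, but it is a pointer and not a precedence rule, and the references back to 3.3.1.2 run against it.

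**Safeguards exist.** Restart requires recovery to grade 0-1 (with an allowance for laboratory values abnormal at entry). Section 3.3.1 sets a two-week limit with Study PI assessment of longer holds. Section 3.7.1.2 lets the investigator stop for unacceptable toxicity, 3.3.9 refers dosing questions to the Study Chair, and under 6.7.1 the team discusses each patient every other week. All of this stands: re-challenge is permitted, not compelled.

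**Everolimus may be fixed on purpose.** Most Table 3-7 rows either resume at the same dose or discontinue, which fits a fixed 5 mg. That stands in part, but then the instructions to reduce everolimus are wrong. The 5 mg reduced dose in 10.2.12.1 is product information for a drug whose recommended dose is given as 10 mg (10.2.12.9); it supplies no lower level here. The references to the suspect drug in 3.3.1.1 and 3.3.1.2 favor changing that drug alone, in which case nothing is lowered.

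**Stronger readings that the documents do not support**
- That the tables stop the drug after every grade 4 event. Everolimus after grade 4 neutropenia and sorafenib after grade 4 hematologic toxicity restart in both places.
- That only the hepatitis B rule (Table 3-4) deals with running out of dose levels. Section 3.3.1 covers patients who need more than two reductions, and Table 3-10 takes such patients off protocol therapy. What is uncovered is a first everolimus reduction.
- That the 21-day delay limits in 3.7.1.5 and 3.3.7, counted from different starting points, let a patient wait until day 28 + 21 = 49 of a cycle. The two-week limit and Study PI review in 3.3.1 come first.

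**Conclusion.** The point holds for four grade 4 entries where one stated rule restarts a drug that another stops, for two sorafenib entries where the reductions differ by 25% and 33% of cycle dose, and for everolimus reductions with no dose to go to. It should be fixed.

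The milligram figures assume a patient at level 1 who takes every scheduled dose. They measure the size of the disagreement, not harm. How many patients are affected cannot be told from the documents. Reach is limited: section 2.4 marks Phase 1 and Groups A and C closed but not Group B, and section 9.4 says that subjects at non-NCI sites were off treatment at Amendment C.

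A reader might infer that the efficacy or safety monitoring design is compromised. It is not: the Simon decision rules and the first-cycle toxicity boundary in section 7.2 do not depend on which restart rule is followed.

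**What to change.** 1. **Section 3.3.1.2:** change the grade 4 row to discontinuation of the suspect drug, leaving hepatitis reactivation to Tables 3-4 and 3-5 and hypertension to Table 3-10. The references from 3.3.3 to 3.3.5 then lead to the same grade 4 action as Table 3-7. Keep the discretion for symptomatic grade 2 events and the nausea/vomiting exception.
2. **Section 3.3.1.1, everolimus:** discontinue for grade 4 thrombocytopenia and grade 4 febrile neutropenia.
3. **Section 3.3.1.1, sorafenib:** adopt the Table 3-9 reductions, two levels for grade 4 and one level for ANC 750-999. Keep the Table 3-9 footnote exceptions.
4. **Keep what is stricter in 3.3.1.1:** its holds, its recovery thresholds (ANC at least 1,500, platelets at least 100,000) and, short of grade 4, its one-level reduction at platelets below 50,000. Bring the looser table entries into line. A one-line rule that the tables always govern looks simpler but would loosen protection. After grade 3 thrombocytopenia Table 3-7 restarts everolimus at platelets of 75,000 and the same dose, and Table 3-9 restarts sorafenib once toxicity is below grade 2.
5. **Everolimus:** either add a lower level to Table 3-2, for example with the 2.5 mg tablet, or replace each reduction with a hold and restart at 5 mg, or discontinuation. State that only the suspect drug is reduced. If a lower level is added, settle in the same amendment the grade 3 rows where Table 3-7 keeps the dose and 3.3.1.1 or 3.3.1.2 lowers it.

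The cost is a text amendment to section 3.3 and its tables, with no added patients or procedures. The downside is that some patients with grade 4 toxicity stop a drug sooner.
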